2 INTRODUCTION

2.1 STUDY RATIONALE

Head and neck squamous cell carcinoma (HNSCC) is responsible for 14,000 deaths annually in the US and has poor survival (50% at 5 years) despite intense treatment including surgery, radiation, and chemotherapy¹. HNSCC is also a disease with significant racial disparities in mortality; African Americans (AAs) have a 51% relative decrease in survival compared with whites². Delays starting postoperative radiation therapy (PORT) after HNSCC surgery are a key driver of high mortality for all HNSCC patients and racial disparities in survival for AAs. As such, the delivery of timely PORT is an appealing therapeutic target to address both issues^{3,4}. We have shown that delayed, non-guideline-adherent PORT initiation (> 6 weeks after surgery⁵) affects 56% of HNSCC patients⁶, is 31% more common in AA HNSCC patients than whites⁶, is associated with an 11% absolute decrease in 5-year survival⁷, and is a key driver of racial differences in mortality³. Our pilot qualitative data suggest that treatment toxicity, travel distance, care coordination, finances, support, knowledge, and communication are barriers to timely, equitable PORT. Delivering timely PORT to all HNSCC patients is critical to prevent excess mortality and racial disparities in survival. Unfortunately, effective interventions to decrease delays and racial disparities starting PORT are unknown^{8,9}, due in part to the lack of understanding of the relevant barriers in this clinical setting. One potential strategy to improve timely, equitable PORT is patient navigation (PN), a barrier-focused intervention that improves the timeliness and racial equity of initial cancer care (screening, treatment initiation)^{10,11}. However, the impact of PN on delays and racial disparities starting PORT, a different point on the cancer care continuum than screening and treatment initiation, is unknown¹². In this proposal, we extend our work to develop and evaluate the feasibility, acceptability, and preliminary clinical impact of NDURE (Navigation for Disparities and Untimely Radiation thErapy), our multi-level, theory-based PN intervention to improve timely, equitable PORT among HNSCC patients.

2.2 BACKGROUND

2.2.1 HEAD AND NECK SQUAMOUS CELL CARCINOMA

HNSCC, which affects the tongue, pharynx, larynx, and neck, is diagnosed in 65,000 patients in the US annually and causes 14,000 deaths per year¹. No screening tests exist for HNSCC, and as a result, more than two-thirds of patients present with locally advanced disease¹. Despite aggressive multimodal therapy consisting of surgery followed by PORT and concurrent chemotherapy⁵, outcomes remain poor with only 50% of patients with locally-advanced HNSCC surviving 5 years¹. HNSCC is also a disease with significant racial disparities in mortality; AAs with HNSCC have a 19% absolute decrease in 5-year survival relative to white HNSCC patients¹³ and a 51% relative decrease in survival².

2.2.2 DELAYS IN CANCER CARE DELIVERY FOR PATIENTS WITH HNSCC

Delays starting PORT contribute to high mortality in HNSCC and racial disparities in survival. Delays in cancer care delivery are a key driver of mortality for HNSCC patients¹⁴ and a source of racial disparities in survival for AAs³. The critical time period for HNSCC patients is the time from surgery to the start of PORT^{8,15}, the only aspect of timely HNSCC care incorporated in National Comprehensive Cancer Network (NCCN) Guidelines (< 6 weeks after surgery)⁵. Delays starting PORT are associated with increased recurrence and decreased survival^{7,16,17}. The 11% improved 5-year survival seen with timely PORT⁷ is large, comparable in magnitude to the benefit seen from adding Cisplatin to PORT in landmark HNSCC trials^{18,19}. Unfortunately, delays starting PORT affect 56% of HNSCC patients⁶. Delays starting PORT also disproportionately affect AAs, who are 31% more likely to experience delays than whites after adjusting

for insurance, income, education, and stage⁶. The high rate of delayed PORT among AA HNSCC patients is a source of preventable mortality and contributes to racial disparities in survival⁷.

2.2.3 BARRIERS TO TIMELY, EQUITABLE PORT AFTER SURGERY FOR HNSCC

The barriers that contribute to delays and racial disparities starting PORT after HNSCC surgery are unknown. AA race, insurance status, prolonged travel distance, and care fragmentation are associated with delayed PORT^{6,20-22}. However, the barriers to timely care delivery at the patient-, provider-, and system-level remain unknown. As a result, the development of targeted, multi-level interventions to address barriers and improve the delivery of timely, equitable PORT for HNSCC patients has been impeded. To prevent continued treatment delays, it is critically important to identify the barriers to delivering timely, equitable PORT.

2.2.4 INTERVENTIONS TO IMPROVE TIMELY, EQUITABLE PORT FOR PATIENTS WITH HNSCC

The care delivery pathway for PORT, which is potentially modifiable through a multi-level intervention, represents an appealing target to decrease mortality and racial disparities in survival for HNSCC patients^{3,4,8}. Unfortunately, despite the large clinical impact of delayed PORT on mortality and racial disparities in survival, no effective interventions have been described^{8,9,23}. A prior study using an atheoretical, provider-centric approach did not find a decrease in the rate of PORT delay²⁴. Improving the timeliness of PORT for white and AA HNSCC patients is crucial to improving survival for all HNSCC patients and decreasing racial disparities in mortality.

2.2.5 RATIONALE FOR PATIENT NAVIGATION TO IMPROVE TIMELY, EQUITABLE PORT

PN is a patient-centered intervention that addresses barriers to cancer care, thereby improving the delivery of timely, equitable cancer screening, decreasing racial differences in post-screening diagnostic resolution, and decreasing care fragmentation^{10,11,25-27}. However, the efficacy of PN in the sequential multimodal cancer care setting (e.g. surgery then PORT) is unknown¹²; care transitions following surgery involve unique care barriers and care coordination challenges²⁸. To address the lack of effective interventions to decrease delays and racial disparities starting PORT after HNSCC surgery⁸, we will develop and test NDURE, our multi-level, theory-based PN intervention to improve timely, equitable PORT among HNSCC patients. The underlying scientific premise is that our NDURE PN intervention has the potential to decrease delays starting PORT among HNSCC patients because PN is most effective in 1) populations with low adherence rates¹⁰ (timely PORT adherence is < 50% overall and <40% among AAs⁶); 2) racial minority populations^{10,29} (delays starting PORT are 31% more common in AAs⁶); and 3) the setting of fragmented care^{10,27} (PORT delivery involves coordinating consults with seven medical specialties²³, care transitions from inpatient to outpatient, and care transitions across healthcare systems [in 51% of cases⁶]).

2.3 RISK/BENEFIT ASSESSMENT

2.3.1 KNOWN POTENTIAL RISKS

Overall, this research study poses no more than minimal risks to participants. There are no physical, financial, legal, social, or cultural, risks to the study participants by joining this study. There are slight psychological risks, as described below. There is a slight risk that subjects may experience adverse

psychological reactions such as anxiety or stress as a result of discussing issues related to cancer or barriers to cancer care. We believe that this risk is minimal. We are using survey items that are commonly used in clinical settings and subjects are likely to have had prior exposure to similar types of questions as part of their medical care. Furthermore, in our past studies with white and AA men and women with HNSCC, the overwhelming majority of respondents have said they found the questions that we have asked related to care have not been upsetting.

There is also a slight risk that confidential information about the participant may be accidentally disclosed as study participants may be asked to provide information considered confidential or private during study interviews. The likelihood of this risk is low as all the investigators have been involved in similar research in the past and have not experienced this problem before due to adequate safeguards.

The decision to participate in this research will be voluntary and individuals may refuse to take part or choose to stop taking part at any time. Participants will also be encouraged to take their time when answering questions and may decline to answer any question at any time. If patients become upset talking about their cancer and the barriers that they faced, they will be offered a referral to the Hollings Cancer Center (HCC) Behavioral Medicine program (which is covered by most health insurance programs) or the HCC Social Worker who will offer links to other HCC and community resources.

2.3.2 KNOWN POTENTIAL BENEFITS

Extrapolating from data about PN in other settings, NDURE may improve the timeliness of PORT after HNSCC surgery and decrease racial disparities in timely HNSCC care. However, although we hypothesize a direct benefit to participants in the NDURE study (in terms of timely HNSCC care), it is unknown whether patients will experience a direct benefit. Data generated from this study are expected to provide benefits to society by providing new knowledge about a practical and scalable strategy for addressing racial disparities in the timeliness of PORT in HNSCC patients. Because timely PORT is associated with decreased rates of recurrence and improved survival, it is expected that if we decrease racial disparities in delays starting PORT, we will improve survival and racial equity in outcomes.

2.3.3 ASSESSMENT OF POTENTIAL RISKS AND BENEFITS

The decision to participate in this research will be voluntary. Participants will be informed that they can stop participating at any time and/or refrain from answering any questions that make them uncomfortable. The interviewers are trained researchers with experience conducting interviews related to cancer. By using survey items that are commonly used in clinical settings (to which subjects have likely had prior exposure as part of their medical care) we will minimize psychological risk. If a participant has a psychological adverse event (AE) talking about his/her cancer and/or the barriers that he/she faced during treatment, the participant will be offered a referral to the HCC Behavioral Medicine program (which is covered by most health insurance programs) or the HCC Social Worker who will offer links to other HCC and community resources as detailed in the Data and Safety Monitoring Plan. Immediate backup and support will be available.

To help ensure and protect privacy of participants and confidentiality of research data for the study, we will assign a unique study ID number to each subject's information in place of his/her name and will label data collection forms with the ID number. All hard copy and electronic files will be stored appropriately using double-locked methods and password-protection. Only the study team members will have access to study records. Participant data will be collected and recorded on either a password-protected electronic data capture format (REDCap) or paper-based forms depending upon patient preference. For the paper collection data method, the data collection form will be labeled only with the participant's unique study ID number, and then stored within locked drawers in a locked office.

The Information on these paper forms will be transferred to a password-protected REDCap database. Any exported data for analysis will be de-identified with all privately identifiable information automatically removed. The key linking subject ID number to an individual will be stored in the password protected REDCap database. The audio recordings from the qualitative interviews will be labeled only with the patient's unique study ID and stored using password-protected files only accessible by the study team through password-protected servers. Once data have been collected, only de-identified data will be exported for analysis. All study personnel will participate in training on protecting the privacy of study participants and personal information will not be disclosed to anyone outside of the research team. Only the principal investigator and study staff participating in data collection or analysis will have access to the data. We have no plan to use laptops, jump drives, CDs/DVDs to transport data.

On the whole, given the minimal risks to the study participants and the potential benefit of the research to participants and society, we believe that the potential reward to participants and society substantially outweighs the risks to the participants.

3 OBJECTIVES AND ENDPOINTS**Table 2. Study Objectives and Endpoints**

NDURE FEASIBILITY STUDY	
Primary	
To assess the feasibility of NDURE among white and AA HNSCC patients with respect to accrual.	Percent of eligible participants who accrue to NDURE (Primary Endpoint)
Secondary	
To assess the feasibility of NDURE among white and AA HNSCC patients with respect to NDURE completion.	Percent of accrued participants who complete NDURE Percent of accrued participants who complete NDURE study assessments
To assess the acceptability of NDURE to white and AA HNSCC patients and HNSCC providers.	PSN-I scale score NDURE Program Evaluation scale score
To characterize navigator caseload and time allocation delivering the NDURE intervention.	Navigator caseload Navigator time allocation (direct) Navigator time allocation (indirect) Navigator time allocation (total)
To describe the preliminary clinical efficacy of NDURE on delays starting PORT among white and AA patients with HNSCC.	PORT delay Racial differences in PORT delay
RCT of NDURE VERSUS USUAL CARE	
Primary	
To evaluate the preliminary clinical impact of NDURE compared with UC on delays starting PORT among white and AA HNSCC patients.	PORT delay, defined per National Comprehensive Cancer Network Guidelines as the initiation of PORT > 6 weeks (42 days) following definitive surgery for HNSCC.
Secondary	
To evaluate the preliminary clinical impact of NDURE compared with UC on time-to-PORT among white and AA HNSCC patients.	Time-to-PORT initiation, defined as the number of days from the date of definitive surgery for HNSCC to the date of initiation of PORT. Treatment package time, defined as the number of days from the date of definitive surgery for HNSCC to the date of PORT completion.
To evaluate the preliminary clinical impact of NDURE compared with UC on racial disparities in delays starting PORT among white and AA HNSCC patients.	PORT delay, defined per National Comprehensive Cancer Network Guidelines as the initiation of PORT > 6 weeks (42 days) following definitive surgery for HNSCC. Time-to-PORT initiation, defined as the number of days from the date of definitive surgery for HNSCC to the date of initiation of PORT.

Table 2. Study Objectives and Endpoints

	Treatment package time, defined as the number of days from the date of definitive surgery for HNSCC to the date of PORT completion.
To evaluate the preliminary impact of NDURE compared with UC on cancer care delivery processes.	Pre-surgical radiation consultation, defined as the attendance by the patient at a consultation with the treating radiation oncologist prior to surgery to discuss radiation therapy in the definitive or adjuvant setting.
	Pre-RT dental extractions, defined as the extraction of indicated carious/non-restorable teeth prior to or during definitive surgery.
	Time from surgery to PORT referral, defined as the time, in days, from the date of the definitive surgical procedure to the date the referral (or postoperative appointment) is placed to discuss adjuvant therapy with the treating radiation oncologist.
	Time from surgery to postoperative appointment with radiation oncology, defined as the time, in days, from the date of the definitive surgical procedure to the date that the patient attends a postoperative appointment with radiation oncology
Exploratory	
To explore the preliminary impact of NDURE compared with UC on completion of adjuvant therapy	PORT duration, defined as the number of days from the initiation of PORT to the completion of PORT among patients who complete the intended course of adjuvant therapy.
	Completion of intended course of PORT, defined as receipt of the planned PORT dose (total Gy)
To explore the preliminary clinical impact of NDURE compared with UC on decreasing barriers to timely PORT.	Percent of total barriers on PBQ that are resolved
	Number of unresolved barriers on PBQ
	Reason for PORT delay
To explore the preliminary behavioral mechanism of action of NDURE.	CTM-15 scale score
	Change from baseline in 
 ISEL-12 scale score Perceived Susceptibility scale score IPQ-R Consequences scale score CASE-Cancer scale score

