8.4.4 EFFICACY ASSESSMENTS

Data for the efficacy assessments described below are gathered from the EMR. For participants who receive care at a non-MUSC facility (and thus whose information is not in the MUSC EMR), records will be requested for the treating facility at the conclusion of adjuvant therapy and scanned into MUSC EMR.

PORT Delay: The initiation of PORT more than 6 weeks (42 calendar days) from the date of the definitive surgical resection.

- If the surgical management of the primary tumor and the neck are staged (i.e. occur on two different calendar days), the date of the definitive surgery for the primary tumor will be used.
- If additional surgical resection is required (e.g. re-resection of positive margins to clear residual disease), the date of the earlier (i.e. attempted definitive) surgical procedure will be used to determine the date of definitive surgical resection.
- Patients who suffer a mortality prior to initiating PORT and > 6 weeks after surgery will be assessed as having a PORT delay.

- Patients who suffer a mortality prior to initiating PORT and \leq 6 weeks after surgery will be non-evaluable for evaluation of the primary endpoint of PORT delay.
- Patients who recur prior to initiating PORT, regardless of the timing of the recurrence relative to 6 weeks postoperatively, will be assessed equivalently to patients who do not recur for the purposes of this endpoint.

Time-to-PORT (TTP): The time, in days, between the date of definitive surgical resection to the initiation of PORT. All of the criteria used to adjudicate the date of the definitive surgical procedure described for the primary outcome measure will be applied to this measure.

- For patients who are alive and have not initiated PORT by 18 weeks (126 days) from surgery, TTP will be censored at this timepoint.
- For patients who suffer a mortality prior to initiating PORT and $<$ 18 weeks after surgery, TTP will be censored at the date of death. (A sensitivity analysis treating death as a competing risk will be performed, as described in Section 9.4)
- For patients who recur prior to initiating PORT, regardless of the timing of the recurrence relative to 18 weeks postoperatively, TTP will be assessed equivalently to patients who do not recur.

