9.2.2 RCT OF NDURE VERSUS USUAL CARE

Power and sample size calculations were performed using PASS v08.0.13, “Inequality Tests for Two Independent Proportions.” The primary endpoint for this pilot RCT is the rate of PORT delay, defined as starting PORT > 6 weeks after surgery. Our primary objective is to compare PORT delay rates between the NDURE and usual care arms. We hypothesize that, compared with patients who receive usual care, patients who receive NDURE will have a decreased rate of PORT delay (initiation of PORT > 6 weeks after surgery). Alternatively, our null hypothesis is that there will be no difference in the rate of PORT delay between NDURE and usual care. We assume the rate of PORT delay in the usual care arm will be 45%⁴⁵ and target an absolute reduction in PORT delay of 20% (rate of PORT delay in the NDURE arm = 25%)²⁴. This effect size is clinically significant and realistic given results in similar (non-randomized) interventions²⁴. Seventy-five patients in each arm yields 83% power to detect a 20% reduction in PORT delay (45% versus 25%) based on a two-sided Z-test with pooled variance of two independent proportions assuming a two-sided $\alpha = 0.1$. Our selection of $\alpha = 0.1$ and $1 - \beta = 0.8$ is based on the desire to emphasize power over type I error at this early stage of development (single-site pilot RCT) to ensure follow-up on promising interventions. Furthermore, given the trial’s design, comparison of PORT delay rates between

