9.4.2 MISSING DATA

- PORT delay status (delay or timely PORT) will be considered 'delayed' for any evaluable patient with missing PORT delay status.
- TTP will be right-censored for evaluable patients who die prior to PORT initiation, are lost to follow-up prior to PORT initiation, or who haven't received PORT by the end of follow-up (18 weeks postoperatively).
- TPT will be right-censored for evaluable patients who die or are lost to follow-up prior to the conclusion of PORT, or who prematurely discontinue their intended course of PORT. TPT will also be right-censored for patients who have not completed PORT by the end of follow-up (18 weeks postoperatively).
- Time from surgery to PORT referral scheduling will be right-censored for evaluable patients who die prior to PORT initiation, are lost to follow-up prior to PORT initiation, or who haven't received PORT by the end of follow-up (18 weeks postoperatively).
- Time from surgery to appointment with radiation oncology will be right-censored for evaluable patients who die prior to PORT initiation, are lost to follow-up prior to PORT initiation, or who haven't received PORT by the end of follow-up (18 weeks postoperatively).

- Analyses of exploratory endpoints will be conducted using complete case analysis.

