9.4.9 EXPLORATORY ANALYSES

For other exploratory endpoints (e.g., health behavior constructs), data will be summarized using frequency and percent for categorical variables and using mean, median, standard deviation, IQR and range for continuous variables. We will construct 90% CIs to provide a measure of uncertainty in estimated proportions and means. Comparisons between trial arms of other exploratory endpoints will be performed using *t*-tests and chi-square tests, or Wilcoxon rank sum and Fisher's exact tests as appropriate. Pre- and post-intervention values of variables measuring the theoretical constructs underlying NDURE (i.e. care coordination, self-efficacy in cancer care, support, and knowledge) will be compared using Wilcoxon sign rank tests. Comparisons between arms of the change in scores will be conducted using Wilcoxon rank sum tests.

For the exploratory endpoints of barrier reduction and unresolved barriers, we will calculate the proportion of unresolved barriers and the frequency of unresolved barriers (respectively) at the end of NDURE, consistent with prior PN studies⁵¹. We will use logistic regression to assess the association between unresolved barriers and the rate of PORT delay (primary endpoint), controlling for randomization stratification variables.

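### The exploratory reason-for-delay endpoint has no stated denominator; its natural reading compares arms only among delayed patients, a group selected by the primary outcome

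*Combined protocol and SAP*

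**What the plan says.** In Section 3, Table 2, "Reason for PORT delay" stands under the comparative objective "To explore the preliminary clinical impact of NDURE compared with UC on decreasing barriers to timely PORT". Other exploratory endpoints, such as PORT duration, are defined there and in Section 8.4.6. This one has no definition, list of categories, analysis set or denominator.

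Section 9.4.9 gives barrier reduction and unresolved barriers their own paragraph. The reason for delay is not named, which leaves the general rule: "Comparisons between trial arms of other exploratory endpoints will be performed using" t-tests and chi-square tests, or their rank-based and exact counterparts. Section 9.4.2 adds: "Analyses of exploratory endpoints will be conducted using complete case analysis". It also counts an evaluable patient with unknown PORT status as delayed.

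Section 8.4.4 defines delay, the primary outcome, as "The initiation of PORT more than 6 weeks (42 calendar days) from the date of the definitive surgical resection".

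**The concern.** A patient who starts PORT on time has no reason for delay. Unless the plan says otherwise, the endpoint exists only in delayed patients, and a between-arm test of it compares two subgroups formed by the primary outcome. NDURE is designed to change that outcome, so randomization no longer protects the comparison.

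The distortion is arithmetical. Delays that NDURE prevents leave the denominator, so any cause that NDURE affects less makes up more of what remains. Section 8.5.1 does not expect NDURE to reduce treatment toxicity itself, and most NDURE components in Section 6.1.1.1 concern education, travel, communication, referral and tracking. Unequal effects across causes are therefore plausible.

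Section 4.2.2 presents this trial as preparation for a definitive one. A real success on coordination could appear in this analysis mainly as a significant shift towards toxicity.

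**Working it through.** **Inputs from the plan (Section 9.2.2).** In per cent: "We assume the rate of PORT delay in the usual care arm will be 45" and "rate of PORT delay in the NDURE arm = 25". Also: "Seventy-five patients in each arm yields 83% power to detect a 20% reduction in PORT delay", with a pooled two-sided Z-test at 0.10. Section 9.4.1 sets 0.05 as the general test level, with 90% CIs.

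**Assumption.** The documents give no breakdown of causes. Two are used here, coordination and toxicity, over a range of splits.

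**1. The plan's own figure.** Pooled rate (0.45 + 0.25)/2 = 0.35. Null SE = √(2 × 0.35 × 0.65/75) = 0.0779. Alternative SE = √((0.45 × 0.55 + 0.25 × 0.75)/75) = 0.0762. Power = Φ((0.20 − 1.645 × 0.0779)/0.0762) = Φ(0.944) = 82.7%. The stated 83% reproduces.

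**2. Expected delayed patients.** 75 × 0.45 = 33.75 in usual care and 75 × 0.25 = 18.75 in NDURE.

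**3. Why the share moves.** Let t be the absolute risk of a toxicity-caused delay, equal in both arms. Its share of delays is t/0.45 in usual care and t/0.25 in NDURE. The ratio is 0.45/0.25 = 1.8 for any t. At t = 10% the shares are 22% and 40%; at t = 15%, 33% and 60%.

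**4. One worked table (the most uneven split).** Usual care has 17 coordination and 17 toxicity delays; NDURE has 2 and 17.
- Delayed patients only: toxicity share 17/34 = 50% versus 17/19 = 89%, Fisher p = 0.006.
- All 75 per arm, toxicity delay: 17/75 = 22.7% in both arms, difference 0.
- All 75 per arm, coordination delay: 17/75 = 22.7% versus 2/75 = 2.7%, Fisher p = 0.0003. The difference is 20.0 points with SE √((0.227 × 0.773 + 0.027 × 0.973)/75) = 0.052, so the 90% CI is 11.5 to 28.5 points.

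**5. Simulation.** Multinomial, 75 per arm, total delay 45% versus 25%, 20,000 trials per row. The last two columns give how often the delayed-only Fisher test is significant with a higher toxicity share in NDURE.

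| Coordination, UC to NDURE | Toxicity, UC to NDURE | Toxicity share, UC vs NDURE | At 0.05 | At 0.10 |
|---|---|---|---|---|
| 22.5% to 12.5% | 22.5% to 12.5% | 50% vs 50% | 1.5% | 3.5% |
| 30% to 15% | 15% to 10% | 33% vs 40% | 5% | 9% |
| 22.5% to 10% | 22.5% to 15% | 50% vs 60% | 7% | 13% |
| 22.5% to 7.5% | 22.5% to 17.5% | 50% vs 70% | 23% | 34% |
| 30% to 10% | 15% to 15% | 33% vs 60% | 40% | 53% |
| 22.5% to 2.5% | 22.5% to 22.5% | 50% vs 90% | 84% | 91% |

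Other runs at 0.05 gave 6–9% for intermediate splits, 24% for the fourth row and 85% for the last. In rows two to four toxicity delays fall in absolute terms, yet the signal points to a higher toxicity share.

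**6. The same trials with all patients as denominator.** In the last two rows, where toxicity-delay risk is equal, Fisher's test on toxicity delay over 75 per arm rejects in about 3% of trials at 0.05 and 6–7% at 0.10, both directions together. Towards more toxicity delay in NDURE, it rejects in about 1.5% and 3%.

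**The case against.** **The test is inferred.** No sentence commits the trial to testing reasons among delayed patients. A timely patient's reason is inapplicable rather than missing, so the complete-case rule does not by itself fix the denominator. An analyst could add a not-delayed category or only tabulate. This stands: the defect is an undefined endpoint whose default route leads to a conditioned test. But nothing in the plan blocks that route.

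**The effect may be even.** Section 8.5.1 hypothesizes that better coordination about toxicity will itself reduce delay. If all causes fall in proportion, the artefact disappears, as the first row shows. This stands, and the size depends on assumed splits.

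**Other analyses cover the ground.** Section 8.5.1 plans a comparison of toxicity events from the barrier questionnaires that is not conditioned on delay, and the same objective has two further barrier endpoints. These help, but they record events and barriers, not the cause to which a delay is attributed.

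**A stronger reading to avoid.** A reader might infer that the analysis would show NDURE causing more toxicity delays. It would not: the share among fewer delays rises, while the number need not (17 and 17 in the worked table). The arm-specific delay rates reported for the primary endpoint would let a careful reader see this.

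**Conclusion.** The point holds as a gap in an exploratory endpoint. With no stated denominator and a general rule that tests between arms, the natural reading conditions on the primary outcome and can signal a shift in causes that reflects only which delays were prevented. At 0.05 the signal towards a higher toxicity share ranges from about 2% of trials under a proportional effect, through 5–9% and 23–24%, to 40% and 84–85% as the effect becomes more uneven. These figures rest on the plan's 45% and 25%, 75 evaluable patients per arm, two causes, and splits that the documents do not supply.

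The documents do not support the inference that the plan has expressly chosen a wrong test, or that any main result is at risk. The primary analysis and the sample size are unaffected, and the 83% power reproduces. The change is worth making because a better analysis of the same data is available at almost no cost.

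**What to change.** In Table 2 and Section 9.4.9:
- Define the endpoint as PORT delay attributed to each listed reason, scored in every patient of the PORT delay analysis set: 1 if delayed for that reason, 0 if timely or delayed for another.
- Include an unknown category for patients counted as delayed because their status is missing (Section 9.4.2).
- Compare arms by the risk difference with a 90% CI for each reason, with all patients of that set as denominator.
- Present the distribution of reasons among delayed patients descriptively.

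The cost is two sentences and slightly more analysis. It uses the reasons that the endpoint already requires the trial to record, so no new data are needed.
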